Venous thromboembolism (VTE) is a common, potentially life-threatening complication in high-risk trauma patients. With emerging evidence demonstrating around 50% of trough serum anti-factor Xa (anti-Xa) concentrations are subtherapeutic and associated with increased VTE risk, the purpose of this pilot study is to evaluate the safety and efficacy of a novel enoxaparin dosing strategy based on anti-Xa values. High-risk patients (e.g., risk assessment profile score ≥ 5) initiated on enoxaparin 30 mg q12h per current trauma team standard of care. Patients will be excluded for renal dysfunction (Cockcroft-Gault calculated creatinine clearance < 30 mL/min or patients on continuous renal replacement therapy), weight < 50 kg or > 150 kg, nephrotic syndrome, platelet count $< 50 \times 10^3$, allergy to heparin, patients on or requiring therapeutic anticoagulation at or within 24 hours of admission, isolated intracranial hemorrhage, known hyperbilirubinemia, pregnancy, or incarceration. Primary outcome is the comparison of antithrombin-III (AT-III), proportion of anti-Xa goal achievement at first, second, and all assessments, and time to goal anti-Xa. Patient outcomes include VTE events, bleeding outcomes, patients with bioaccumulation, and risk factors for low anti-Xa.

Purpose of Study

The purpose of this pilot study is to compare two enoxaparin dosing strategies: BID dosing and a dosing strategy based on anti-Xa values in high-risk trauma patients. Specific aims include: 1) to compare the extent of reduced AT-III activity between patients with anti-Xa ≥ 0.1 IU/mL and < 0.1 IU/mL upon initial assay and determine the proportion of patients who reach goal anti-Xa and time to goal anti-Xa between two dosing strategies: enoxaparin 40 mg every 12 hours (with consideration to increase to 50 mg every 12 hours if recheck anti-Xa is not at goal; see section 6) and enoxaparin 30 mg every eight hours; 2) to compare anti-Xa adjusted enoxaparin-dosing strategies based on VTE, bleeding rates, transfusion requirements, drug discontinuation rate and bioaccumulation, and 3) to determine patient-specific factors that correlate to subtherapeutic anti-Xa such as serial AT-III activity, weight, body mass index, age, cumulative fluid administration and thromboelastography (TEG).

Background

Background and Significance

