VTE are associated with a high morbidity and mortality. Optimal LMWH dosing has not been established for critically injured patients who have altered pharmacokinetics due to altered volume of distribution and metabolism, variable age and weight, and potential decreases in AT-III. Subtherapeutic serum anti-Xa trough concentration has been associated with increased risk for VTE. This pilot clinical investigation has the potential to revolutionize enoxaparin dosing and VTE prevention through anti-Xa guided dosing. Thorough evaluation of risk factors for reduced anti-Xa may provide a focused assessment of patients requiring anti-Xa assessment and subsequent dose adjustments. Overall, optimal enoxaparin dosing will result in fewer VTE events without increasing bleeding risk with an anti-Xa driven adjustment. Improved patient outcomes, expansion of scientific knowledge, and development of VTE prevention protocols may result.

Potential Risks, Discomforts, and Inconveniences

Level of Risk

VTE risks with inadequate prophylaxis have been previously justified above. Risks of increased enoxaparin doses include major and minor bleeding events. Risks will be mitigated by appropriate exclusion of patients with low body weight and increased serum creatinine / decreased creatinine clearance. Serum assays for risk of bioaccumulation will be performed weekly with subsequent dose reduction. Additionally, patient serum creatinine and creatinine clearance will be assessed daily by the trauma team with appropriate therapy modification should patient's renal function worsen. Patients with a 50% change in serum creatinine or an absolute change in serum creatinine by 1 mg/dL will be removed from the study. If these changes in renal function occur after patient has received initial laboratory assessment (i.e., anti-Xa; AT-III; TEG) will be included in the primary outcome analysis.

Blood volume loss due to serum anti-Xa, TEG, and AT-III assay as described above is minimal (2.7 mL x 2). Patients requiring peripheral vein access for serum assays will be at risk for pain/discomfort, bruising, fainting, and infection from phlebotomy sites.

Data Safety Monitoring Plan

Collected data will be screened for adverse events. [name] will act as medical monitor and review collected data and all adverse events to ensure patient safety.

Data Analysis

Primary Endpoints

1. Initial AT-III activity between the control group and the intervention group.

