2. Proportion of patients reaching goal anti-Xa between group 1 and group 2 overall, at first repeat assessment, and at second repeat assessment.
3. Median time to achievement of goal anti-Xa between group 1 and group 2.

Secondary Endpoints

1. Patient outcomes to be compared between control and intervention groups including all VTE events (i.e., pulmonary embolism; upper extremity deep venous thromboembolism [DVT]; proximal lower extremity DVT; distal lower extremity DVT), major bleeding (i.e., hemoglobin decrease of ≥ 2 g/dL in a 24 hour period requiring ≥ 2 units of packed red blood cells while on enoxaparin; worsened or new intracranial hemorrhage while on enoxaparin; repeat surgical intervention due to hemorrhage while on enoxaparin), minor bleeding (minor gastrointestinal bleeding [coffee ground emesis with or without < 2 units packed red cell transfusion needed while on enoxaparin]; interruption of study drug by trauma team; other overt bleeding not characterized a major while on enoxaparin), total transfusion requirements after 48 hours until discharge or admission day 28.
2. Proportion of patients with enoxaparin bioaccumulation (defined as an anti-Xa ≥ 0.3 IU/mL at any assay) between group 1 and 2.
3. Risk factor determination for low anti-Xa.

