Statistical analyses will be performed using SAS version 9.3 (SAS Institute, Inc., Cary, NC). An intention-to-treat model will be used for data analysis. Patients excluded due to change in renal function will be included in the primary outcome analysis, but not patient outcome analyses for VTE and bleeding outcomes. Nominal data will be reported using frequencies of occurrence and proportions as appropriate. Continuous data will be reported using means and standard deviations or medians and ranged as appropriate per distribution. Hypothesis testing for nominal data will be performed using the Fisher's exact test or chi square test as required based on sample size. Continuous data will be compared using student's t-test/ANOVA or rank sum/Kruskal-Wallis ANOVA for normally distributed and non-normally distributed data, respectively. A p-value < 0.05 will designate statistical significance. Time-to-event analyses will be compared as appropriate and presented as Kaplan-Meier curves. Multivariate logistic regression will be performed for low anti-Xa risk determination. All values with a p-value < 0.2 will be included in the model. Serum AT-III, weight, and age will be forced into the model, regardless of p-value.

A total of 200 patients will be enrolled. Assuming that 50% of patients will have an undetectable anti-Xa on enoxaparin 30 mg every 12 hours, we hypothesize the intervention group will have an absolute reduction in AT-III activity of 10% compared to the control group if the control group has a mean AT-III activity of 80% with a standard deviation of 25%. Secondly, we hypothesize that there will be an absolute difference of 27% in the proportion of patients who achieve goal anti-Xa between group 1 and group 2, assuming 50% of group 1 achieves goal. To achieve an 80% power with an alpha of 0.05 for both outcomes, goal enrollment is 200 patients (table 2).

Table 2. Power analysis for each outcome

AT-III activity difference between control and intervention			
Absolute difference in means	Standard Deviation		Sample Size
10%	25%		200
10%	30%		286
10%	10%		34
20%	30%		74
20%	10%		12
Anti-Xa ≥ 0.1 IU/mL attainment between group 1 and group 2			
Group 1 Proportion	Group 2 Proportion		Sample Size
50%	77%		100
50%	75%		116
60%	80%		164
80%	90%		398
70%	80%		588
VTE reduction between study groups			
Estimate Source	Control Proportion	Intervention Proportion	Sample Size
Malinoski ¹⁵	37%	11%	98

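### Four primary tests bear on the randomised comparison, each judged at p < 0.05 with no lead test or order, although the sample size counts attainment as one test

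*Combined protocol and SAP*

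**What the plan says.** The Primary Endpoints list in Data Analysis has three numbered items:

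- Item 1: "Initial AT-III activity between the control group and the intervention group". One comparison, between patients classified by their own first anti-Xa result.
- Item 2: "Proportion of patients reaching goal anti-Xa between group 1 and group 2 overall, at first repeat assessment, and at second repeat assessment". Three comparisons of the randomised groups.
- Item 3: "Median time to achievement of goal anti-Xa between group 1 and group 2". One comparison of the randomised groups.

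The opening summary gives the same set as the primary outcome: AT-III, then "proportion of anti-Xa goal achievement at first, second, and all assessments, and time to goal anti-Xa".

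The statistical paragraph sets a single threshold, "A p-value < 0.05 will designate statistical significance". It gives no adjustment, testing order or lead endpoint. The sample-size paragraph then states "To achieve an 80% power with an alpha of 0.05 for both outcomes, goal enrollment is 200 patients". Its two outcomes are AT-III activity and attainment of goal anti-Xa (50% versus 77%). Neither that paragraph nor Table 2 names the assessment at which attainment is counted, and time to goal has no power calculation.

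**The concern.** The sample-size paragraph and the endpoint list disagree on how many primary tests there are. The first counts two outcomes. The second yields five comparisons, four of them on the same randomised question. With no lead test, nothing says which result answers that question, and the 5% error rate stated for attainment does not describe four looks at group 1 versus group 2.

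The four tests are also not interchangeable. Under Intervention, a group 1 patient who is still below goal at the repeat assay has the dose raised, while group 2 has no upward step. The first repeat therefore compares the regimens as randomised. The second repeat and the overall proportion compare a strategy with escalation against one without. The results could differ, and the plan does not say which would count.

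**Working it through.** **Step 1. Reproduce the plan's sample sizes** (two-sided 0.05, 80% power).

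- AT-III, difference 10, SD 25: n per group = 2 × (1.960 + 0.842)² × 25² / 10² = 98.1, so 99 per group and 198 in total. The t-based version gives 100 per group, the 200 in Table 2. Power at 100 per group is 80.7%.
- Attainment, 50% versus 77%, pooled rate 63.5%: n per arm = [1.960 × √(2 × 0.635 × 0.365) + 0.842 × √(0.50 × 0.50 + 0.77 × 0.23)]² / 0.27² = 48.7, so 49 per arm and 98 in total. Table 2 gives 100. Power at 50 per arm is 81.0%.

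Both reproduce, each as one test at the full 0.05.

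**Step 2. Count the tests.** 1 (AT-III) + 3 (attainment) + 1 (time to goal) = 5, of which 4 are randomised.

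**Step 3. Reference points, each test at exactly 5%.**

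- All five independent: 1 − 0.95⁵ = 22.6%.
- The four randomised tests perfectly correlated, AT-III independent: 1 − 0.95² = 9.75%.

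**Step 4. Simulate under no difference, 50 versus 50.** The following are assumptions, because the documents do not settle them:

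- overall attainment means goal at any assay (the summary speaks of all assessments, the endpoint list of overall);
- time to goal is compared by log-rank (the plan says only that time-to-event data are compared as appropriate);
- within-patient latent correlation is varied;
- the goal rate per assay is 50% or 63.5%;
- AT-III is independent of the randomised comparison, so the five-test figure is 1 − 0.95 × (1 − four-test figure).

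Results with two assays, 20,000 runs per row. Five-test figures were computed before rounding.

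| Goal rate | Correlation | Chi-square, 4 tests | Chi-square, 5 tests | Fisher, 4 tests | Fisher, 5 tests |
|---|---|---|---|---|---|
| 50% | 0.3 | 13.4% | 17.7% | 9.4% | 13.9% |
| 50% | 0.5 | 12.9% | 17.3% | 9.2% | 13.7% |
| 50% | 0.7 | 11.8% | 16.3% | 8.3% | 12.9% |
| 50% | 0.9 | 10.6% | 15.1% | 7.7% | 12.3% |
| 63.5% | 0.3 | 13.0% | 17.4% | 9.1% | 13.6% |
| 63.5% | 0.5 | 12.1% | 16.5% | 8.7% | 13.3% |
| 63.5% | 0.7 | 11.1% | 15.6% | 8.0% | 12.6% |
| 63.5% | 0.9 | 9.6% | 14.1% | 7.2% | 11.9% |

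With three assays, a 50% goal rate, chi-square and correlations 0.3, 0.6 and 0.8 (6,000 runs), four tests give 14.8%, 13.4% and 12.1%, and five give 19.0%, 17.7% and 16.5%.

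Over two or three assays and correlations 0.3 to 0.95, the four randomised tests give about 9-15% with chi-square and about 7-11% with Fisher. All five give about 11-20%. The top is reached with four assays (20.1% at goal rate 50%, correlation 0.3, chi-square). The bottom comes from Fisher with very high correlation.

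**Step 5. Which test is likelier.** At goal rates of 50-77% with 50 per arm, the smallest expected count is 0.23 × 50 = 11.5, so chi-square is the more likely choice for the individual assessments.

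**The case against.** The strongest reply has four parts.

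- **The study is called a pilot**, and its stated use is to inform a later dosing protocol. This lowers the stakes. It does not remove the gap, because the plan states formal hypotheses, a significance threshold and power.
- **AT-III does not belong in the same family.** It is measured before randomisation and asks a prediction question, so a false positive there supports no claim about a regimen. This stands. The figure that matters for the randomised claim is the four-test one.
- **The size depends on assumptions.** This also stands. A reader might infer a single figure of 17-19% for a false primary claim. The documents do not support that: it needs moderate correlation, chi-square throughout, a particular number of assays and a definition of overall attainment, and it pools AT-III with the randomised tests. The enrolment figures show up to six trough assays after randomisation (assays 3 to 8), and the plan permits Fisher's exact test.
- **The plan does not say that any one significant test would establish superiority.** That is correct, and such a rule should not be attributed to it. The difficulty is that the plan states no decision rule at all.

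A reader might also infer that the power calculation refers to the first repeat. Neither the sample-size paragraph nor Table 2 says so, and 50% versus 77% could as well describe overall attainment.

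**Conclusion.** The point holds. Four primary tests address one randomised question at an unadjusted 0.05, while the sample-size statement budgets for one. If the regimens do not differ, the chance of at least one significant result among the four is roughly double to triple the nominal 5% with chi-square and somewhat less with Fisher, under the assumptions listed in the check. The exact figure is an illustration. The excess over 5% appears in every setting examined. Adding AT-III raises the total further, but that total mixes a non-randomised question with a randomised one and should not be the headline. The plan should be changed, at moderate priority: the defect affects how a positive result may be read, and the repair needs no new data.

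**What to change.** Before analysis:

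1. In the opening summary, item 2 of the Primary Endpoints and the sample-size paragraph, name the one attainment comparison to which 50% versus 77% applies. Make it the sole primary test of the randomised question at 0.05.
2. Make the other two attainment comparisons and time to goal secondary. Either test them in a stated fixed order at 0.05, only if the lead test is significant, or report them descriptively. Define overall attainment and name the test for time to goal.
3. Keep AT-III as a separate, non-randomised question at 0.05. State that error is held at 5% within each question, which is 1 − 0.95² = 9.75% across both if they are independent.

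The sponsor should choose the lead by the question it wants answered: the first repeat for the regimens as randomised, or the second repeat or overall for strategies that include the group 1 escalation step.

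**Cost.** The endpoint list in the protocol changes, so this is more than a wording edit to the analysis section. If the lead test fails, no confirmatory claim can be made on the later tests. No patients or assays are added, and power for the lead test stays about 81% if 50% versus 77% applies to it. By contrast, a Bonferroni split over five tests (0.01 each) would cut that power to about 59% and need about 146 randomised patients to restore 80%.

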Increased VTE rates have been seen in patients with subtherapeutic anti-Xa values. Malinoski¹⁵ found that of 54 patients on enoxaparin 30 mg every 12 hours, 27 (50%) had subtherapeutic anti-Xa troughs and a statistically significant higher DVT rate than those with appropriate levels (37% vs. 11%, $p = 0.026$). Mean peak anti-Xa values were also lower in the subtherapeutic group (0.17 ± 0.1 IU/mL vs. 0.27 ± 0.1 IU/mL, $p < 0.001$); however, peak anti-Xa values were not different in those with and without DVT (0.23 ± 0.12 IU/mL vs. 0.23 ± 0.1 IU/mL, $p = \text{NS}$). A subsequent enoxaparin anti-Xa dose-adjusted protocol targeting peak anti-Xa levels between 0.2 – 0.4 IU/mL showed 18 (29.5%) of 61 patients on 30 mg twice-daily enoxaparin were at goal anti-Xa after the third dose.¹⁶ Only 5 (8.2%) patients, all in the therapeutic peak anti-Xa group, had a trough anti-Xa > 0.1 IU/mL. VTE events occurred in three patients in the entire study cohort (4.9%). Of the 27 patients with dosage adjustments, 22 (81.5%) patients received enoxaparin 40 mg twice daily, four patients received 50 mg twice daily (14.8%), and 1 patient received 60 mg twice daily (3.7%). Of note, there were no major bleeding events, which is not surprising given the anti-Xa peak goal is much lower when compared to standard therapeutic dosing goals (e.g., 0.5 – 1.1 IU/mL). Finally, a before-and-after study evaluated an anti-Xa adjusted dalteparin dosing strategy in high-risk (risk assessment profile [RAP] ≥ 5) trauma patients.¹⁷ High-risk patients were initiated on dalteparin 5000 units daily with a 12-hour anti-Xa value drawn after the first dose in the post-protocol group. If the 12 hour anti-Xa was < 0.1 IU/mL, the dose was increased to 5000 units twice-daily. Low trough anti-Xa was seen in 51% of post-group patients. VTE was lower in the post-protocol group (7.0% vs. 12.8%, $p = 0.009$) and higher in the subgroup of patients with a subtherapeutic trough anti-Xa (14.4% vs. 5.4%, $p = 0.05$). Therefore, anti-Xa adjustment of LMWH may result in fewer VTE events. No difference in blood transfusion after the first 48 hours was noted, suggesting appropriate safety with an anti-Xa driven dosing protocol for dalteparin.

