Robinson ¹⁴ (1 mg/kg q24h; n = 19)	0.40	-	-	-	-

Study Justification

Ideal enoxaparin dose for VTE prevention in high-risk trauma patients is unknown. Predictors and explanations for low anti-Xa are also unknown. With emerging evidence demonstrating around 50% of trough anti-Xa concentrations are subtherapeutic and associated with increased VTE risk, the purpose of this study is to compare AT-III serum concentrations as a predictor of low anti-Xa. Secondly, the study will compare two enoxaparin dosing. Ultimately, this information can be used to develop an optimum protocol for patient-specific enoxaparin dosing for VTE prevention to improve patient outcomes.

METHODS**Study design**

This is an investigator-initiated, single-center, prospective, non-blinded, randomized controlled trial. Multi-system trauma patients between 18-80 years old admitted to the University of Cincinnati Medical Center (UCMC), an urban American College of Surgeons-verified Level 1 trauma center will be identified by the Trauma Surgery team. The trauma team will inform study personnel of these patients once enoxaparin is initiated. These patients will be screened for inclusion in the study. Patients who meet inclusion criteria will be administered informed consent by study personnel in their rooms. Patients in the surgical intensive care unit (SICU) and on the surgical floor are eligible for enrollment if all other inclusion and exclusion criteria are met. Informed consent will be obtained prior to enrollment. Goal enrollment is 200 patients with 100 patients in the control group and 50 patients in each randomization group.

Research data collection/study procedures

Patients will be screened daily by the trauma team. Research personnel will be alerted to potential patients for enrollment.

Intervention

Serum AT-III and anti-Xa will be drawn eight hours after the third dose of enoxaparin 30 mg q12h. Serum assays after at least the third dose should approximate drug steady state trough concentrations. Patients with a serum anti-Xa ≥ 0.1 IU/mL will remain on enoxaparin 30 mg every 12 hours and will be the control group. Patients with undetectable anti-Xa (intervention groups), defined as a trough anti-Xa < 0.1 IU/mL, will be randomized to receive either:

- a. Enoxaparin 40 mg every 12 hours (group 1)
- b. Enoxaparin 30 mg every eight hours (group 2)

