Droege ¹⁷	14.5%	5.5%	390
2013 UCMC Trauma Registry VTE	5.5%	2.5%	1468
2013 UCMC Trauma Registry VTE	5.5%	4.5%	6576

Data storage and confidentiality (include sample storage if applicable)

A single, central, electronic database will be constructed using Microsoft Excel® for storing all study-related data (attached). The database will be password protected such that only authorized study personnel can access the data. Data will be maintained in a confidential manner with regular reminders of the need for confidentiality provided from the senior investigator. A single subject log will be kept for matching patient study number, initials, medical record number, and admission date (attached). Once assigned to the log, patients will only be evaluated using their de-identified, study number. Data entered into the electronic database will be de-identified.

Once the study has been completed, the electronic database will be maintained in a locked office, per the IRB specifications. Only study personnel will have access to the data. Once the IRB-approved time has elapsed, all materials will be destroyed.

Study Population

Patients admitted to the UCMC trauma service are eligible for enrollment.

Inclusion Criteria

- a. Patients with an anticipated length of stay of at least 72 hours
- b. High-risk patients initiated on enoxaparin 30 mg every 12 hours per the existing VTE prophylaxis protocol
 - a. High-risk is defined as patients with a risk assessment profile (RAP) ≥ 5 .¹⁹
 - b. Trauma team VTE prophylaxis protocol contraindications to chemical prophylaxis include
 - i. Intracranial bleeding (e.g., chemical prophylaxis contraindicated within 24 hours of documented stable head computed tomography [CT]),
 - ii. Incomplete spinal cord injury with hematoma within 24 hours post-injury
 - iii. Ongoing hemorrhage
 - iv. Uncorrected coagulopathy
 - v. \geq grade IV liver or spleen injury
 - vi. Intraocular injuries.
- c. Age 18 – 80 years old

Exclusion Criteria

- a. Renal dysfunction (creatinine clearance < 30 mL/min or patients on continuous renal replacement therapy)
- b. Weight < 50 kg or > 150 kg
- c. Platelet count $< 50 \times 10^3$
- d. Allergy to heparin or low molecular weight heparins
- e. Patients on therapeutic anticoagulation at admission or requiring it within 24 hours of admission
- f. Isolated intracranial hemorrhage
- g. Known hyperbilirubinemia (defined as serum bilirubin > 6.6 mg/dL; interferes with the anti-Xa chromogenic assay)

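### Two of the four VTE rows in Table 2 give Control the event rate of patients with low anti-Xa, whereas this trial's control group is the patients with adequate anti-Xa

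*Combined protocol and SAP*

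**What the plan says.** **Groups (Methods, Intervention).** "Patients with a serum anti-Xa ≥ 0.1 IU/mL will remain on enoxaparin 30 mg every 12 hours and will be the control group". For the rest, "Patients with undetectable anti-Xa (intervention groups), defined as a trough anti-Xa < 0.1 IU/mL, will be randomized to receive either" of two changed regimens. Nobody below 0.1 IU/mL is assigned to stay on the starting regimen.

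**VTE comparison (Data Analysis, Secondary Endpoints, item 1).** "Patient outcomes to be compared between control and intervention groups including all VTE events". The statistical text applies Fisher's exact or chi-square tests to nominal data at p < 0.05 and states no covariate adjustment for VTE.

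**Planning rates (Table 2, block "VTE reduction between study groups").**

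| Row | Source | Control | Intervention | N |
|---|---|---|---|---|
| 1 | enoxaparin study | 37% | 11% | 98 |
| 2 | dalteparin study | 14.5% | 5.5% | 390 |
| 3 | site registry | 5.5% | 2.5% | 1468 |
| 4 | site registry | 5.5% | 4.5% | 6576 |

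**Origin of rows 1 and 2 (Background and Significance).** In the enoxaparin study, half of 54 patients "had subtherapeutic anti-Xa troughs and a statistically significant higher DVT rate than those with appropriate levels (37% vs. 11", the last figure being 11%. In the dalteparin study VTE was "higher in the subgroup of patients with a subtherapeutic trough anti-Xa (14.4% vs. 5.4", the last figure being 5.4%.

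**The concern.** Rows 1 and 2 take their Control rate from patients with low anti-Xa. The trial's control group is the opposite stratum. The contrast behind these rows is low anti-Xa left alone against anti-Xa brought to goal, and the design has no arm for the first half of it.

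The comparison that will be run sets patients who began with adequate levels against patients who began with low levels and then had their regimen changed. Its result mixes the effect of adjustment with the baseline difference in risk. A reader who takes Table 2 at face value would look for less VTE under intervention than under control. Full success of dose adjustment could then be read as no benefit, and partial success as harm. The Potential Benefits section expects fewer VTE events from anti-Xa-driven adjustment, and this contrast cannot test that expectation.

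**Working it through.** **1. Reproduce the plan's figures.** Inputs are the Table 2 proportions, alpha 0.05 (two-sided assumed, since the plan does not say) and 80% power. With d = |p1 − p2| and p̄ their mean, per group:

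n = [1.96·√(2p̄(1−p̄)) + 0.842·√(p1(1−p1) + p2(1−p2))]² / d²

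with continuity correction n′ = (n/4)·[1 + √(1 + 4/(n·d))]².

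- Row 1: p̄ = 0.24, d = 0.26. n = (1.1838 + 0.4842)² / 0.0676 = 41.16; n′ = 48.54, so 49 per group and **98** in total. Stated: 98.
- Row 2: p̄ = 0.10, d = 0.09. n = (0.8315 + 0.3530)² / 0.0081 = 173.2; n′ = 194.8, so 195 per group and **390** in total. Stated: 390. The Background's 14.4% and 5.4% give 388.

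The arithmetic of both rows is right. What fails is the mapping of rates to groups.

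**2. Map the rates to this trial's groups.**

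| Rate | Patients it describes (Background) | Their group in this trial | Column in Table 2 |
|---|---|---|---|
| 37% | subtherapeutic trough | Intervention | Control |
| 11% | appropriate levels | Control | Intervention |
| 14.4% (14.5% in the table) | subtherapeutic trough | Intervention | Control |
| 5.4% (5.5% in the table) | comparator, not named | presumably Control | Intervention |

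Rows 3 and 4 rest on "2013 UCMC Trauma Registry VTE", with no anti-Xa status given. The reversal cannot be claimed for them.

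**3. What the planned comparison could show.** No section gives a VTE rate for initially low patients on the adjusted regimens, so this is a range under stated assumptions: control has 11%, unadjusted low patients have 37%, and adjustment removes a share f of the 26-point excess. Intervention rate = 37% − f × 26 points.

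Power at 100 versus 100 = Φ{[d·√100 − 1.96·√(2p̄(1−p̄))] / √(p1(1−p1) + p2(1−p2))}. For f = 50%: (1.300 − 1.053) / 0.529 = 0.466, so 68%.

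| f | Control | Intervention | Intervention minus control | Power, 100 vs 100 | Total N, Table 2 method |
|---|---|---|---|---|---|
| 0% | 11% | 37% | +26 points | 99% | 98 |
| 25% | 11% | 30.5% | +19.5 | 93% | 154 |
| 50% | 11% | 24% | +13 | 68% | 296 |
| 75% | 11% | 17.5% | +6.5 | 26% | 968 |
| 100% | 11% | 11% | 0 | no difference to detect | – |

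The power column has no continuity correction. Replacing d by d − 1/100 gives about 99, 90, 61 and 20%. Either way, power in the first four lines is power to find *more* VTE under intervention. Table 2 assumes 26 points in the other direction.

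**4. A true reduction below control.** It would need the intervention rate to fall under that of the adequate group. Halving 11% to 5.5%, purely as an illustration, needs N 856 by the table's method; power with 200 patients is about 29% (uncorrected).

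**5. The dalteparin row.** According to the Background, that protocol itself raised the dose when the 12-hour level was below 0.1 IU/mL, so 14.4% may already be a rate after adjustment. The denominators are also unclear: 0.51 × 14.4% + 0.49 × 5.4% = 10.0%, against the 7.0% reported for the post-protocol group. For this reason step 3 uses only the enoxaparin study.

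**The case against.** The strongest reply is that little hangs on these rows. VTE is a secondary endpoint in a study called a pilot. The text states hypotheses and power only for AT-III activity and anti-Xa attainment, and N = 200 rests on those. Rows 2 to 4 ask for 390 to 6576 patients, so the table as a whole hardly advertises 200 as enough for VTE. Aim 2 in Purpose of Study can be read as group 1 against group 2, which is randomized. All of this stands and limits the weight of the point. It does not remove it: the control-versus-intervention VTE test is listed under Secondary Endpoints, and the table's heading calls it a reduction.

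A reader might also infer more than the documents support:

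- *That all four VTE rows are reversed.* The registry rows carry no anti-Xa status, so only two can be shown to be.
- *That the dalteparin row gives the VTE excess to expect if adjustment does nothing.* Its low patients may already have been adjusted, and its comparator is not named.
- *That intervention can never fall below control.* These patients are assigned more drug per day than control, and no section excludes a lower rate. None supports one either.
- *That the chance of a significant result is simply alpha.* That is so only if the two rates are exactly equal; partial removal gives the range in the working.

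**Conclusion.** The point holds for two of the four VTE rows. Their arithmetic reproduces exactly, but their group labels run opposite to the trial's definitions, and the reduction they describe has no comparator arm. On the enoxaparin study's rates, the planned comparison would show between 26 points more VTE under intervention (no effect of adjustment) and no difference (all excess removed).

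That range assumes that 11% and 37% carry over to this population, that DVT rates stand in for all VTE, and that the groups reach 100 and 100. It is an illustration, not a forecast. The conclusion that the contrast is non-randomized and confounded by baseline anti-Xa needs none of these assumptions.

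The plan should be corrected before VTE results are interpreted. A reader might go on to conclude that the trial is wrongly sized; the documents do not support that, because VTE does not set the sample size.

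**What to change.** 1. In Table 2, delete the 37%/11% and 14.5%/5.5% rows. Alternatively, relabel their columns by anti-Xa status (subtherapeutic; comparator), note that they do not correspond to this trial's control and intervention groups, and add that the dalteparin figures come from a protocol that itself adjusted the dose.
2. In Data Analysis, state that the control-versus-intervention VTE comparison is non-randomized, separated by baseline anti-Xa, descriptive, and not evidence for or against VTE reduction by dose adjustment.
3. State there that group 1 versus group 2 is the only randomized VTE contrast, and tie it to aim 2.

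The cost is wording only. Enrollment, procedures, dosing and N = 200 stay as they are. The plan gives up an implied VTE-reduction claim on a secondary endpoint.
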